## 1.0 PROTOCOL SUMMARY AND/OR SCHEMA

This is a phase II, single-institution, open-label trial of enzalutamide 160 mg PO QD in patients with androgen receptor (AR)+ ovarian, fallopian tube or primary peritoneal cancer with measurable disease and one, two or three prior cytotoxic treatments. All enrolled patients will be treated with enzalutamide 160 mg PO QD until progression of disease (POD), unacceptable toxicity or withdrawal from study. All treatments will be administered in the outpatient setting.

\*A maximum of 19 enrolled patients will have 3 prior therapies

\*\* In cases where multiple blocks are available staining will be performed on unstained slides from 3 separate blocks. If  $\geq 5\%$  AR tumor staining is seen on  $\geq 1$  slide the tumor will be considered to be AR+.

## 2.1 OBJECTIVES AND SCIENTIFIC AIM

Primary Objective:

- To estimate the proportion of women with AR(+) ovarian, primary peritoneal, or fallopian tube cancer who survive progression free for at least 6 months and the proportion of patients who have objective tumor response (complete or partial response) by RECIST 1.1 criteria when treated with enzalutamide 160 mg PO QD.

Secondary Objective:

- To determine the frequency and severity of adverse events as assessed by NCI CTCAE version 4.0 in women with AR (+) ovarian, primary peritoneal, or fallopian tube cancer treated with enzalutamide 160 mg PO daily.

Exploratory Objective:

- To perform optional tumor biopsies following treatment with enzalutamide, in order to determine the effect of treatment with enzalutamide on androgen receptor expression
- To observe the effect of enzalutamide on serum testosterone and estradiol levels in women with AR+ ovarian, primary peritoneal, or fallopian tube cancer.

### **3.0 BACKGROUND AND RATIONALE**

#### **3.1 Androgen Receptor and Ovarian Cancer**

Ovarian cancer is the second most common gynecologic malignancy and the leading cause of death among women with gynecologic malignancies. There are an estimated 21,990 new cases and 15,460 cancer-related deaths from ovarian cancer in the United States annually [1]. Approximately 75% of women with epithelial ovarian cancer present with advanced (stage III or IV) disease. Standard treatment for women presenting with advanced ovarian cancer includes cytoreductive surgery followed by combination chemotherapy with platinum and taxane agents [2]. The majority of these women will recur and be treated with multiple lines of single-agent cytotoxic chemotherapy. Progression-free survival following first, second and third remission are 10.2, 6.4 and 5.6 months respectively[3]. Long-term survival among women diagnosed with advanced-stage ovarian cancer remains < 30%. Additional options for recurrent and persistent disease are clearly needed [4, 5].

Androgen receptors (ARs) are found in 67-90% of cases of epithelial ovarian cancer, and are more prevalent than estrogen (32-55% of cases) or progesterone receptors (46-52% of cases) in this disease [6-10]. Historically, studies targeting androgen inhibition in ovarian cancer using GnRH agonists or AR antagonists have shown a response rate of 0-22% and stable disease in 8-70% of women [11-20]. Our group at MSKCC published a negative phase II study of goserelin and bicalutamide consolidation therapy in patients with 2 or more prior therapies in 2007; androgen inhibition in ovarian cancer has largely been ignored since that time [21].

However, all clinical studies of androgen inhibition in ovarian cancer to date have been performed in an unselected population of patients with multiple lines of prior treatment. Recent preclinical data shows that primary cultures of AR+ ovarian cancer cells show an increase in cell division when exposed to androgen, and that this activity is reversed when androgen is inhibited[22]. In addition, androgen receptor positivity has been shown to decrease following chemotherapy, indicating that patients with multiple lines of prior treatment may be less likely to be AR+ and therefore less likely to respond to antiandrogen therapy.

### **3.2 Enzalutamide**

Enzalutamide is a novel small molecule androgen-receptor antagonist selected for its activity against cells overexpressing the androgen receptor [23]. Enzalutamide has a novel mechanism of action that is unlike that of bicalutamide and has been shown in preclinical studies to provide a more complete suppression of the antiandrogen receptor pathway than bicalutamide. Enzalutamide slows growth and induces cell death in AR expressing cells via three complementary actions. Enzalutamide blocks testosterone binding to the androgen receptor, impedes nuclear translocation of the androgen receptor, and inhibits binding of DNA. Preclinical data have demonstrated that enzalutamide is superior to bicalutamide in each of these three actions.

In a mouse xenograft model of prostate cancer using an androgen receptor overexpressing cell line, Enzalutamide treatment resulted in a dose-dependent reduction in tumor volume ( $p < 0.05$  and  $p < 0.01$  for mid-and high-dose groups vs. vehicle, respectively). Enzalutamide treatment resulted in unmeasurable tumors in 1/7 animals in the low-dose group and 3/7 animals in the high-dose group. As expected, bicalutamide had little effect on tumor growth.

Enzalutamide binds with high affinity to the human androgen receptor ( $K_i = 13$  nM). Other targets for which measurable enzalutamide binding was detected included the human progesterone receptor with a 50% inhibitory concentration ( $IC_{50}$ ) of 10-25  $\mu$ M and the rat gamma amino butyric acid-gated chloride channel ( $IC_{50} = 2.6$   $\mu$ M;  $K_i = 2.1$   $\mu$ M [1.0  $\mu$ g/mL]). No significant binding was detected with the remaining 70 receptors.

### **3.3 Previous Human Experience with Enzalutamide**

The safety and tolerability of enzalutamide have been evaluated in numerous clinical studies in both healthy adult male volunteers and in male patients with prostate cancer. The duration of exposure ranges from a single dose to more than 4 years. The estimated safety, PK, and tolerability are based primarily upon the data collected from the completed Phase 1-2 study (S-3100-1-01).

Study S-3100-1-01 was an open label, dose-escalation study of enzalutamide in 140 patients with advanced prostate cancer. Patients were treated with enzalutamide at doses of 30 to 600mg/day until disease progression or intolerable side effects developed.

In this study, enzalutamide was absorbed rapidly after oral administration, with the median time to Cmax after a single dose occurring at 1 hour (range 0.42 to 4 hours postdose). No major deviations from dose proportionality were observed over the dose range of 30 to 600mg. Due to the long t1/2 (~5.8 days), it took approximately 1 month to reach steady state. With daily oral administration, enzalutamide accumulated approximately 8.33-fold relative to a single dose. The peak-to-trough ratio was approximately 1.25, indicating that the average difference between the peak and trough concentrations was ≤ 25%. As a result of the low daily fluctuations, plasma profiles at steady-state resembled a constant infusion. The trough values in individual patients remained constant beyond Day 28 of chronic therapy, suggesting time-linear PKs once steady state was achieved.

Grade 3/4 adverse events reported by at least 3% of patients were fatigue (14%), anemia (4%), and back pain (3%). Fatigue was the most frequently reported adverse event, with dose-dependent increases of Grade 3 fatigue (0% at 150mg/day, 9% at 240 mg/day, 15% at 360mg/day and 20% at 480 mg/day). At doses of 240 mg and above, an increasing proportion of patients needed dose reductions for fatigue (1 of 29 patients [3%] who received 240mg/day, 3 of 28 patients [11%] who received 360mg/day and 5 of 22 patients [23%] who received 480mg/day, compared with 0 of 59 patients who received 30, 60 or 150 mg/day). After dose reductions, the symptoms resolved. Only 1 patient discontinued treatment due to fatigue with an onset coinciding with prostate-specific antigen (PSA) rise. The dose of 240mg/day was defined as the maximum tolerated dose.

At the highest dose of 600mg/day, 2 of 3 patients had dose-limiting toxicities (DLT) (seizure, rash, respectively), both of which led to treatment discontinuation. Other causes of treatment discontinuation included rash (n=1 at 480 mg/day), and a myocardial infarction after 15 weeks of 360mg/day in a patient with a history of diabetes, hypertension, and hypercholesterolemia. One witnessed seizure at 360 mg/day and a possible seizure at 480 mg/day were also reported. No deaths and no other drug-related serious adverse events were reported.

### **3.3 Enzalutamide and Prostate Cancer**

The AFFIRM trial, a randomized, double-blind, placebo-controlled, phase III trial, evaluated whether enzalutamide could prolong overall survival in men with castration resistant prostate cancer who progressed following docetaxel-based chemotherapy. Patients who had previously received ≤ 2 regimens of docetaxel-based chemotherapy were randomized 2:1 to enzalutamide 160mg PO QD or placebo. Treatment with corticosteroids was allowed but not required. Between September 2009 and November 2010 1,199 patients were randomized. Based on a planned interim analysis at 520 death events, the Independent Data Monitoring Committee recommended the study be unblinded and placebo patients offered MDV3100 due to a significant OS benefit (p<0.0001; HR 0.631) . The estimated mean OS was 18.4 months for MDV3100 treated patients compared to 13.6 months for placebo treated men, a median OS difference of 4.8 months[24].

The most common ( $\geq 5\%$ ) grade 1-4 adverse reactions included asthenia or fatigue, back pain, diarrhea, arthralgia, hot flush, peripheral edema, musculoskeletal pain, headache, upper respiratory infection, muscular weakness, dizziness, insomnia, lower respiratory infection, spinal cord compression and cauda equina syndrome, hematuria, paresthesia, anxiety, and hypertension. Grade 3-4 adverse reactions were reported in 47% of patients treated with enzalutamide and in 53% of those on placebo.

Enzalutamide was subsequently FDA approved on August 31, 2012 for treatment of patients with metastatic castration-resistant prostate cancer who have previously received docetaxel.

### **3.4 Androgen Inhibition and Breast Cancer**

The AR is expressed in 60-80% of breast cancers and has been implicated in breast cancer biology [25]. High androgen levels are associated with an increased risk of developing breast cancer in postmenopausal women and androgens have been shown to initiate tumor formation via the AR in animal models [26, 27].

A study evaluating the effects of leuprorelin acetate in women with breast cancer demonstrated responses (complete or partial) predominantly in premenopausal women [28]. In this study, hormone receptor status was unknown on any of the postmenopausal patients. The majority of premenopausal patients had ER + disease. Hot-flashes and weight gain were the only reported toxicities.

In another study, goserelin was administered to 118 pre-/peri-menopausal women of varying ER status. With the exception of hot-flashes, the therapy was well tolerated. The overall response rate was 45% and median time to progression was 59 weeks [29].

Abiraterone acetate is a steroidal inhibitor of CYP17 that blocks two important enzymatic activities in the synthesis of testosterone. A phase I study of abiraterone acetate in estrogen receptor (ER) positive or AR positive advanced breast cancer patients has been completed. A total of 25 patients were treated in 6 patient cohorts at doses between 250mg and 2000mg PO daily. At the 1000mg and 2000mg dose levels good suppression of estradiol, testosterone, DHEA and DHEAS were seen. Two patients (both ER+/AR+) were previously treated with multiple lines of hormonal therapy but continued on treatment with abiraterone acetate for > 11 months. One of these patients achieved a radiographic partial response. It was concluded that abiraterone acetate is well tolerated in advanced breast cancer patients with preliminary evidence of anti-tumor activity at the 1000mg dose level [30].

### **3.5 Rationale for Current Study**

In summary, recent data shows that AR+ primary cultures of ovarian cancer cells proliferate in the presence of androgen and this proliferation is reversed by androgen inhibition. AR expression may be decreased following exposure to multiple lines of cytotoxic chemotherapy. Abiraterone acetate has shown promising results in patients with

AR+ breast cancer; however due to suppression of adrenally produced androgen it can produce severe side effects related to hypokalemia, hypertension and edema. In the ovarian cancer population, where malignant ascites is common, toxicities related to increased edema from abiraterone and prednisone would be significant.

Prior targeted therapies for treatment of ovarian cancer have shown response rates of 0%-21% and PFS at 6 months of 6.5%-40.3% in patients with recurrent or advanced ovarian cancer and a history of 1-2 prior cytotoxic therapies (Table 1).

Table 1.

Study	Agent	Target	N	Response Rate	PFS at 6 Months
170-C	Gefitinib	EGFR	27	3.7%	14.8%
170-D	Bevacizumab	VEGFA	62	21%	40.3%
170-E	Imatinib	Bcr-abl/c-kit/PDGFR	56	1.8%	16.1%
170-F	Sorafenib	VEGFR/PDGRR/RAF	59	3.4%	23.7%
170-G	Lapatinib	EGRR/HER2neu	26	0.0%	7.7%
170-H	Vorinostat	HDAC	27	3.7%	7.4%
170-J	Enzastaurin	PKC-beta	27	7.4%	11.1%
170-K	Mifepristone	PR	22	4.5%	13.6%
170-M	Dasatinib	Scr/bcl-abl/c-kit	34	0%	20.6%
170-N	A6	uPAR	31	0%	20.6%
170-P	AMG-102	HGF(c-met)	Suspended after first stage		

Earlier studies examining alternative methods of androgen inhibition in ovarian, primary peritoneal, and fallopian tube cancer have all been performed in an unselected population of women, typically with multiple prior lines of therapy. Drawing on recent advances, the present study will be performed in a selected population of women with AR+ advanced ovarian, primary peritoneal, or fallopian tube cancer ( $\geq 5\%$  by IHC) with measurable disease. Enrolled patients will have had only one, two or three prior cytotoxic therapies. All enrolled patients will be treated with enzalutamide 160 mg PO QD until progression of disease (POD), unacceptable toxicity or withdrawal from study. Based on the prior response rates that have been seen with targeted therapy of recurrent or advanced ovarian cancer (Table 1), and the relatively benign side effect profile of enzalutamide, we will consider this treatment worthy of further study if there is an observed response rate of 12.5% or an observed 6 month PFS interval is seen in 22.5% of patients. Given that enzalutamide 160 mg PO has not previously been administered to women with ovarian cancer this study will utilize a safety lead-in. If  $\geq 5$  out of the first 15 patients develop a DLT during the first 28 days of treatment then the study will be put on hold. If this does not occur then enrollment will continue.

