### 4.3 Intervention

Prior to initiation of treatment patients will sign a screening informed consent form for AR IHC testing. If archival tissue is not available then the patient must consent to a biopsy. In cases where multiple blocks are available staining will be performed on unstained slides from 3 separate blocks. If  $\geq 5\%$  AR tumor staining is seen on  $\geq 1$  slide the tumor will be considered to be AR+. Only those patients found to have  $\geq 5\%$  AR by IHC will be eligible for treatment.

All enrolled patients will be treated with enzalutamide 160mg PO QD. Study drugs will be self-administered by patients. A cycle is 28 days. Patients will be required to maintain a pill diary to record each dose of drug taken (see **Appendix A**). All toxicities will be graded using CTCAE version 4.0. Toxicities will be evaluated during physician assessments performed every 2 weeks during the first cycle and every 4 weeks during subsequent cycles of treatment with enzalutamide.

Patients will continue to receive study treatment until POD (as defined by RECIST 1.1), unacceptable toxicity or withdrawal of consent.

Dose modifications will be allowed as described in **Section 9**.

Enrollment will proceed following a safety lead-in of 15 patients. If  $\geq 5$  patients develop any of the following events classified as dose-limiting toxicity (DLT) during the **first 28 days** of treatment the study will be halted and the PI will examine the toxicity profile and determine whether lower doses will be added. DLT is defined as:

- Any event consistent with a seizure of any grade
- Grade  $\geq 3$  diarrhea, nausea, or vomiting that does not improve to Grade 1 within 14 days of initiating standard of care therapy
- Grade  $\geq 3$  decreased platelet count with associated bleeding
- Grade  $\geq 3$  absolute neutrophil count (ANC) that persists for 7 or more days or that is associated with fevers (febrile neutropenia)
- Any other  $\geq$  Grade 3 non-hematologic toxicity determined to be related to study drug

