## 9.2 Overview of Dose Adjustments of Enzalutamide for Toxicity

Report of seizure will result in immediate cessation of enzalutamide. A patient who experiences a DLT (other than seizure) during the safety lead-in phase may be allowed to continue study treatment following adequate recovery and appropriate dose modification. Any dose modification of enzalutamide requires consultation with the study sponsor.

- If Grade 1 or 2 toxicities occur, give supportive care per institutional guidelines. No enzalutamide dose reduction should occur.
- If  $\geq$  Grade 3 toxicities occur that are considered potentially related to enzalutamide, including headache, nausea, vomiting or diarrhea, hold enzalutamide until the toxicity resolves to  $\leq$  Grade 1, unless baseline is grade 2, then until returns to baseline.
- If enzalutamide is held for  $\leq$ 28 days it may be restarted at the same or a reduced dose at the discretion of the study sponsor (or designee).
- If enzalutamide is held for  $>$ 28 days the patient should be removed from study treatment

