## 14.2 Safety Lead-in

In order to reduce patient risk, we will examine in detail the first cycle DLT and other safety data for the first 15 patients before enrolling the rest of the study's patients. A patient is considered toxicity-free for the purpose of the trial if he/she completes the first cycle of therapy (28 days) without experiencing a DLT as defined as:

- And event consistent with a seizure of any grade
- Grade  $\geq 3$  diarrhea, nausea, or vomiting that does not improve to Grade 1 within 14 days of initiating standard of care therapy
- Grade  $\geq 3$  platelet count with associated bleeding
- Grade  $\geq 3$  absolute neutrophil count (ANC) that persists for 7 or more days or that is associated with fevers (febrile neutropenia)
- Any other  $\geq$  Grade 3 non-hematologic toxicity determined to be related to study drug

If a patient experiences a DLT during cycle 1, but is able to continue on protocol following dose holding/dose reduction, they will still be considered a DLT.

Based on Gönen [31], we utilize a Bayesian interpretation for  $\theta$  (the probability of DLT at a planned dose;  $\sim \text{Beta}(\alpha, \beta)$ ). The number of observed DLTs ( $X_s$ ) in the safety lead-in

cohort of  $N_s$  patients is assumed to follow a binomial distribution ( $P(X_s | \theta) \propto \theta^{X_s} (1 - \theta)^{N_s - X_s}$ ). Therefore, the posterior distribution of  $P(\theta | X_s)$  is  $\text{Beta}(\alpha + X_s, \beta + N_s - X_s)$ . A uniform prior as

$Beta(\alpha=1, \beta =1)$  is used to reflect the uncertainty value for  $\theta$  as suggested by Gönen [31].

Let  $N_s =15$ , the probability that  $\theta$  exceeds various targets (i.e. 0.2, 0.3, 0.4) given the observed DLT patients' number ( $P(\theta|X_s)$ ) can be calculated. They are listed in the following table:

DLT # in the 15 safety lead-in patients	$P(\theta>0.2)$	$P(\theta>0.3)$	$P(\theta>0.4)$
0	0.028	0.003	0.000
1	0.141	0.026	0.003
2	0.352	0.099	0.018
3	0.598	0.246	0.065
4	0.798	0.450	0.167
5	0.918	0.660	0.329
6	0.973	0.825	0.527
7	0.993	0.926	0.716
8	0.999	0.974	0.858
9	1.000	0.993	0.942
10	1.000	0.998	0.981
11	1.000	1.000	0.995
12	1.000	1.000	0.999
$\geq 13$	1.000	1.000	1.000

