Based on the table above, if we observe 0/15 patients with DLTs in the safety lead-in cohort, there is 0.003 chance that  $\theta$  exceeds 0.3; whereas, if 5/15 patients with DLTs are observed, the chance that  $\theta$  exceeds 0.3 increases to 0.660. Given these probabilities at the end of safety lead-in, we can make informed decisions regarding the appropriateness of the choice of the following trial (i.e. if  $\geq 5$  DLTs observed in the safety lead-in cohort, the trial will be halted immediately and the PI will examine the toxicity profile and determine whether lower doses will be added).

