## 16.3 Data and Safety Monitoring

The Data and Safety Monitoring (DSM) Plans at Memorial Sloan-Kettering Cancer Center were approved by the National Cancer Institute in September 2001. The plans address the new policies set forth by the NCI in the document entitled —Policy of the

National Cancer Institute for Data and Safety Monitoring of Clinical Trials|| which can be found at: <http://cancertrials.nci.nih.gov/researchers/dsm/index.html>. The DSM Plans at MSKCC were established and are monitored by the Office of Clinical Research. The MSKCC Data and Safety Monitoring Plans can be found on the MSKCC Intranet at: <http://mskweb2.mskcc.org/irb/index.htm>

There are several different mechanisms by which clinical trials are monitored for data, safety and quality. There are institutional processes in place for quality assurance (e.g., protocol monitoring, compliance and data verification audits, therapeutic response, and staff education on clinical research QA) and departmental procedures for quality control, plus there are two institutional committees that are responsible for monitoring the activities of our clinical trials programs. The committees: *Data and Safety Monitoring Committee (DSMC)* for Phase I and II clinical trials, and the *Data and Safety Monitoring Board (DSMB)* for Phase III clinical trials, report to the Center's Research Council and Institutional Review Board.

During the protocol development and review process, each protocol will be assessed for its level of risk and degree of monitoring required. Every type of protocol (e.g., NIH sponsored, in-house sponsored, industrial sponsored, NCI cooperative group, etc.) will be addressed and the monitoring procedures will be established at the time of protocol activation.

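### The safety lead-in has one numerical hold, five DLTs in 15 patients, so 3 in the first 5 or 4 in the first 8 requires no pause; two early review boundaries would narrow the gap cheaply

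*Combined protocol and SAP*

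**What the plan says.** Section 3.5 puts the study on hold if five or more "out of the first 15 patients develop a DLT during the first 28 days of treatment then the study will be put on hold". Below that count, "If this does not occur then enrollment will continue". Section 4.3 repeats the rule ("Enrollment will proceed following a safety lead-in of 15 patients"), and so does 14.2 Safety Lead-in, which adds that the trial halts immediately at five or more DLTs and that the principal investigator then considers lower doses.

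The stated plan is that "we will examine in detail the first cycle DLT and other safety data for the first 15 patients before enrolling the rest". The posterior table in 14.2 is computed for 15 patients only, and the text applies it at the end of that cohort: "Given these probabilities at the end of safety lead-in, we can make informed decisions".

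Other safeguards exist, but none carries a count that would hold the trial:

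- Section 4.3: "Toxicities will be evaluated during physician assessments performed every 2 weeks during the first cycle".
- Section 9.2: study drug is held for potentially related toxicity of grade 3 or worse and stopped for seizure, both in the affected patient. In addition, "Any dose modification of enzalutamide requires consultation with the study sponsor".
- Section 16.3: "there are two institutional committees that are responsible for monitoring the activities of our clinical trials programs".
- Section 17.3: SAE reporting to the IRB.

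**The concern.** Section 3.5 gives the reason for the lead-in: this dose has not been given to women with ovarian cancer. Early protection is therefore its purpose. As written, new women can keep starting treatment until a fifth DLT is recorded. A cluster of three in the first five, or four in the first eight, obliges nobody to pause, and any earlier hold rests on judgement. The DLT definition includes seizure of any grade, which stops the drug in that patient but triggers nothing at trial level.

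Under the plan's own model, both clusters give a higher posterior probability of excess toxicity than the 5/15 result that does stop the trial. What is at stake is how many women are exposed before a review if the dose is poorly tolerated in this population.

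**Working it through.** **Inputs from the plan.** Beta(1,1) prior, binomial likelihood, 15 lead-in patients, hold at 5 or more DLTs (Section 14.2 Safety Lead-in); accrual of 3 to 6 patients per month (Section 14.2, sample size).

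**1. Reproduce the plan's figure.** The posterior is Beta(1+x, 1+n−x). Its upper tail at t equals P(Bin(n+1, t) ≤ x). For x=5, n=15, t=0.3 this is P(Bin(16, 0.3) ≤ 5) = 0.660, as printed. Tabulated rows 0 to 12 all agree to rounding.

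**2. Same model, earlier counts.** P(θ>0.3):

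| DLTs/patients | P(θ>0.3) | Hold required now? |
|---|---|---|
| 3/5 | 0.930 | no |
| 4/8 | 0.901 | no |
| 3/6 | 0.874 | no |
| 4/9 | 0.850 | no |
| 4/10 | 0.790 | no |
| 5/15 | 0.660 | yes |

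**3. Check that does not use the prior.** Binomial chance of reaching each count:

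| True DLT rate | 3+ of 5 | 4+ of 8 | 5+ of 15 |
|---|---|---|---|
| 0.05 | 0.116% | 0.037% | 0.061% |
| 0.08 | 0.453% | 0.220% | 0.497% |
| 0.10 | 0.856% | 0.502% | 1.272% |
| 0.20 | 5.79% | 5.63% | 16.42% |
| 0.30 | 16.3% | 19.4% | 48.5% |

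From about 0.08 upwards both clusters are rarer by chance than 5/15. For 3/5 the order reverses below about 0.075. For 4/8 it reverses only between 0.02 and 0.03, where all these chances are below 0.01%.

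**4. Sensitivity to the prior.** Under an assumed sceptical Beta(1,19), the posterior is Beta(1+x, 19+n−x), and P(θ>0.2) is 0.264 at 3/5, 0.348 at 4/8 and 0.300 at 5/15. The 3/5 ordering does not survive this prior; the 4/8 ordering does.

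**5. Effect of adding two boundaries.** The existing rule is read favourably, as a halt at the fifth DLT. The comparison rule holds at 3 or more DLTs in the first 5, 4 or more in the first 8, or 5 or more in 15, each applied as soon as its count is reached. Exact patient-by-patient enumeration, with outcomes known at once:

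| True rate | Women treated, now → added | Saved | Chance of hold, now → added |
|---|---|---|---|
| 0.10 | 14.97 → 14.88 | 0.1 | 1.3% → 2.0% |
| 0.20 | 14.58 → 14.03 | 0.6 | 16.4% → 18.9% |
| 0.30 | 13.40 → 12.16 | 1.2 | 48.5% → 51.1% |
| 0.40 | 11.65 → 9.76 | 1.9 | 78.3% → 79.7% |
| 0.50 | 9.84 → 7.50 | 2.3 | 94.1% → 94.5% |

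If the plan instead means one review after all 15 are treated, the current figure is 15 at every rate and the savings are larger.

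**6. Recognition delay.** Simulation, 40,000 runs, assumed Poisson arrivals at 3 or 6 per month. Women saved at 3 and 6 per month:

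| True rate | Uniform over 28 days | At day 14 or 28 visit | All at day 28 |
|---|---|---|---|
| 0.3 | 1.15, 0.97 | 1.13, 0.88 | 1.08, 0.77 |
| 0.4 | 1.79, 1.58 | 1.78, 1.47 | 1.76, 1.35 |
| 0.5 | 2.25, 2.03 | 2.22, 1.93 | 2.26, 1.84 |

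At 0.20 the saving is 0.31 to 0.49 across these settings; at 0.10 it is 0.05 to 0.09.

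**The case against.** The uniform prior dominates at such small numbers. By the same calculation P(θ>0.3) is 0.910 after 1/1 and 0.916 after 2/3, so exceeding 0.660 cannot by itself justify a stop. The plan applies its table only at 15 patients, and the 0.90 level and three-DLT minimum behind the proposed boundaries are not the plan's. This stands: the posterior comparison alone is not decisive. The binomial tails carry the argument without a prior, though only from a DLT rate of about 0.08.

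A high DLT rate is also unlikely. Section 3.3 reports no grade 3 fatigue at 150 mg in men and a maximum tolerated dose of 240 mg; Section 11.1 reports seizures in 0.6% of 800 men at 160 mg. At rates of 0.20 or below the saving is about half a woman or less. This stands too, and it limits the weight of the point.

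In a single-centre, open-label trial with two-weekly first-cycle visits, three DLTs in five women would be seen, and drug is held or stopped in each affected patient. The institutional monitoring plans were not supplied and might contain a threshold. These measures permit a pause; nothing in the supplied text requires one.

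Finally, some DLTs need 7 days of persistence or 14 days without improvement to qualify, so a late event could be confirmed after day 28, beyond the delays modelled. That could reduce the saving.

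**Conclusion.** The concern holds as a gap in early protection. The plan does not contradict itself, and its table is correct. The gain is mainly an earlier hold rather than more holds: allowing for recognition by day 28, roughly one woman spared at a DLT rate of 0.3 and 1.3 to 1.8 at 0.4, while the chance of a hold rises by 2.6 and 1.4 points respectively. At 0.10 the saving is under 0.1. These figures assume independent DLTs at a constant rate, a current rule that halts at the fifth DLT, and the stated accrual. The point is worth considering because the remedy is cheap and serves the lead-in's stated purpose; it does not undermine the trial.

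**What to change.** In Sections 3.5, 4.3 and 14.2, add two holds for review: 3 or more DLTs among the first 5 patients to start treatment, and 4 or more among the first 8. Count patients in order of starting, whether or not they have finished cycle 1, and act as soon as the count is reached. Keep 5 of 15 as the last boundary, and print the early ones beside the posterior table.

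These boundaries are our proposal. They correspond to P(θ>0.3) of at least 0.90 with at least three DLTs required. They narrow the gap without closing it: 3/6, 4/9 and 4/10 would still prompt no numerical hold.

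The cost is protocol wording and two table rows, with no extra patients or tests. The downside is a review pause in some runs that would have ended below 5 of 15: 0.7 points more at a true rate of 0.10, 2.5 at 0.20 and 2.6 at 0.30.
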